We propose to repeat the trial using an identical design and intervention, but including only urine collected from long term care facilities (LTCF). The control arm is standard of care. We hypothesize that the modified reporting intervention will also reduce treatment of ASB in the LTCF population, without causing harm.

Objectives

Research Question: Among patients with positive urine cultures collected from LTCF reported by Health Sciences microbiology laboratory, would restricted reporting, as compared to standard reporting, lead to a reduction in the rate of inappropriate antibiotic therapy without an increase in bacteremia or death over 30 days?

Trial design

Randomized controlled trial, 2 parallel groups with equal allocation, superiority analysis.

Methods: Participants, interventions, and outcomes

The proposed study is a randomized trial of two methods of laboratory reporting in which physicians are the main research participants. At the time of positive urine culture results, the specimen will be randomized in the laboratory using computer generated random numbers placed into serially numbered sealed, opaque envelopes, into two equal groups. One group will receive modified reporting, and the other group will receive standard reporting of bacterial identification and susceptibility. Physicians receiving modified reports will have the option to call the laboratory to receive complete results, or not. Complete results will be released by laboratory information system to physicians who call to request them. Physicians will be informed about the study prior to initiation, and debriefed about the study after the results have been collected.

The primary efficacy outcome is proportion of appropriate antibiotic therapy prescribed by physicians, based on published diagnostic criteria for ASB and UTI among catheterized patients. Appropriate therapy is defined as any treatment for UTI, or no treatment for ASB. Inappropriate therapy is defined as no treatment for UTI, or treatment for ASB. The primary safety outcome is rate of bacteremia and death. The study investigators will determine the

diagnosis based on a chart assessment to determine if the patient has UTI, CA-UTI, ASB or CA-ASB.

The definition of UTI in LTCF will be based on 2017 Canadian LTCF surveillance guidelines.(12) For residents without an indwelling catheter, criteria 1 and 2 must be present with no other identified source of infection, OR criteria 2 and 3.

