elderly with high care needs. One centralized microbiology laboratory performs all testing for the city.

Inclusion and exclusion criteria for participants

Consecutive positive urine cultures collected from patients admitted to LTCF will be included. All methods of urine collection will be included (midstream, in-and-out catheterization, indwelling catheter). Exclusion criteria will be urine cultures not collected from LTCF patients, pregnancy, antibiotic treatment at the time of collection, and patients known to have blood neutrophils <1.0 within 7 days.

Interventions

The modified report states “This POSITIVE urine culture may represent asymptomatic bacteriuria or urinary tract infection. If urinary tract infection is suspected clinically, please call the microbiology laboratory at [name] between 0900 to 2300, or the microbiology technologist on-call at [name] at night, for identification and susceptibility results.” The standard report provides bacterial count, bacterial identification and bacterial susceptibility results.

The report is provided to the physician approximately 24 hours after receipt of the specimen, when cultures have been examined after overnight incubation. The intervention is a single report, so it is not possible to discontinue the intervention, or change allocation during the trial. There will no other influence on concomitant care or treatment.

Outcomes

Primary efficacy outcome:

Proportion of appropriate antibiotic therapy prescribed by physicians. Appropriateness is determined by investigators based on chart review, based on diagnosis of UTI or ASB. Appropriateness is determined within two days from positive urine culture.

Secondary efficacy outcomes:

Proportion of calls from physicians requesting complete report

Primary safety outcomes:

Mortality rate over thirty days from positive urine culture.

Bacteremia rate over thirty days from positive urine culture.

Adverse event rate over seven days from positive urine culture.

Participant timeline

TIMEPOINT	STUDY PERIOD				
	Enrolment	Allocation	Post-allocation		
	Day -1	Day 0	Day 2	Day 7	Day 30
ENROLMENT:					
Eligibility screen	Urine specimen received at microbiology laboratory	Urine culture result reported to physician	Physician treatment decision made	Safety assessment	Safety assessment
Allocation	X				
INTERVENTIONS:					
Reporting		X			
ASSESSMENTS:					
Appropriateness			X		
Adverse Events			X	X	X
Bacteremia			X	X	X
Mortality			X	X	X

Sample size

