In the previous trial of the same intervention, modified reporting increased the appropriateness of treatment from 29/55 (52.7%) to 44/55 (80.0%) ($p=0.002$), for an absolute difference of +23%.(11) Accepting a risk of type 1 error of five percent, and a risk of type 2 error of twenty percent, the study will require $2N=90$ patients. To account for missing data, recruitment will be increased to 100 patients.

The microbiology laboratory receives 130 urine specimens per day, with 30 percent reported as significant growth (40 specimens per day). Ten percent are submitted from LTCF (4 positive specimens per day). In the previous trial, approximately 40% of eligible specimens were excluded based on exclusion criteria. Recruitment of 100 specimens will require approximately 40-60 days.

The statistical test to be used is a comparison of proportions between two groups (T test, two-sided analysis). Because true diagnosis may be biased by lack of access to clinical information, an intention to treat analysis including all patients randomized will be performed.

Recruitment

Every urine specimen received for culture during the study period will be assessed for inclusion.

Allocation:

Sequence generation

Randomization sequence will be generated without blocking or stratification (Research Randomizer 4.0)(13).

Allocation concealment

Reporting assignments will be placed into serially numbered, sealed, opaque envelopes.

Implementation

Allocation sequence will be generated by investigators. Investigators will enroll specimens and assign specimens to reporting interventions.

Blinding

Trial participants (physicians) will not be blinded to the intervention because the laboratory report will reveal the intervention. Investigators will be blinded to assignment. Data analyst will not be blinded to assignment.

Data collection methods

After randomization and reporting, a physician investigator will assess inpatients for the true diagnosis of UTI or ASB at two days after reporting. Health records will be accessed including demographics, symptoms, treatment decisions and outcomes.

If patients are discharged from hospital before thirty days, primary care physicians will be contacted by phone for additional clinical information. If patients die before thirty days, available data will be analyzed.

Frequency of physician calls requesting complete reporting will be recorded.

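### Investigators generate the allocation list, enrol and assign, and no independent list-holder is named, so neither concealment at entry nor the stated investigator blinding is assured

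*Combined protocol and SAP*

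**What the plan says.** Under Allocation, the Implementation paragraph states: "Allocation sequence will be generated by investigators. Investigators will enroll specimens and assign specimens to reporting interventions". The concealment device is given just above it: "Reporting assignments will be placed into serially numbered, sealed, opaque envelopes". The sequence is neither blocked nor stratified. No other person is given custody of the list or the filling of envelopes, and no step requires eligibility to be recorded before an envelope is opened.

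The Blinding section says that investigators are blinded to assignment and that the data analyst is not. The Outcomes section has investigators decide, from chart review, whether treatment was appropriate, which is the primary efficacy outcome. The Auditing section rules out any audit of conduct.

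On timing, the Methods section says: "At the time of positive urine culture results, the specimen will be randomized in the laboratory". In the Participant timeline, as the table reads here, the Allocation row is marked under Day -1, the column captioned "Urine specimen received at microbiology laboratory". The same table heads its Day 0 column Allocation. The Interventions section adds: "The report is provided to the physician approximately 24 hours after receipt of the specimen".

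**The concern.** Allocation concealment depends on the person who decides entry not knowing the next assignment. An envelope protects against people who have not seen its contents; it gives no protection against the person who produced the list. The protocol gives list generation, enrolment and assignment to one named group and does not divide the tasks within it.

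Two things are at stake. The first is entry. If the next arm is known while exclusions are being decided, specimens can be admitted or turned away selectively. Neither an intention-to-treat analysis nor blinded assessment can repair that afterwards, and with no eligibility log and no audit it would be hard to detect. The safety comparison is the more fragile one: the previous trial had two deaths against one and two bacteremias against one, so one diverted resident could alter it.

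The second is outcome assessment. Someone who made the list or opened the envelope cannot be blinded to the assignment, and investigators also classify each case as infection or asymptomatic bacteriuria.

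**Working it through.** **1. The passages side by side**

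| Step | Who, per protocol | Section |
|---|---|---|
| Generate sequence | Investigators | Implementation |
| Hold list, fill envelopes | Not stated | Allocation concealment |
| Assess eligibility | Not stated (passive voice) | Recruitment |
| Enrol and assign | Investigators | Implementation |
| Judge primary outcome | Investigators | Outcomes |
| Blinded to assignment | Investigators | Blinding |

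The last row agrees with the generating and assigning rows only if different investigators do these tasks. The protocol does not say that they do.

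**2. Number of entry decisions**

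The Sample size section plans on the previous trial, where "approximately 40% of eligible specimens were excluded based on exclusion criteria". With 4 positive specimens a day from long-term care, 100/(4 × 0.6) = 42 days, which reproduces the low end of the stated 40-60 days. So the 40% rate is the protocol's own planning figure. It implies 100/(1 − 0.40) = 167 positive specimens screened and 167 − 100 = 67 turned away.

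This is a rough guide only. The previous trial also excluded indwelling catheters, intensive care and age under 18. Here catheter specimens are included, and the other two are not listed as exclusions.

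**3. What selective entry could do (illustration)**

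Assumptions: no true effect; 50 analysed per arm; appropriate treatment 29/55 = 52.7% in both arms; and a fraction f of would-be inappropriate specimens is turned away when the next report is the modified one. The documents give no value for f.

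- Modified-arm rate: p_M = 0.527 / (0.527 + 0.473 × (1 − f)).
- Specimens turned away to reach 50: 50 / (0.527 + 0.473 × (1 − f)) − 50.
- Chance of a significant result favouring modified reporting: the upper-tail probability of the two-sided 5% test of two proportions, n = 50 per arm, normal approximation. This is 2.5% when f = 0.

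| f | p_M | Spurious difference | Turned away | False positive favouring modified |
|---|---|---|---|---|
| 5% | 54.0% | 1.3 points | 1.2 | 3.3% |
| 10% | 55.3% | 2.6 points | 2.5 | 4.5% |
| 20% | 58.2% | 5.5 points | 5.2 | 8.0% |
| 30% | 61.4% | 8.7 points | 8.3 | 13.9% |

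Worked line for f = 10%: 0.527/(0.527 + 0.473 × 0.9) = 0.527/0.953 = 0.553; 55.3 − 52.7 = 2.6 points; 50/0.953 − 50 = 2.5 specimens. For scale, the planned difference is 80.0 − 52.7 = 27.3 points. The illustration is generous to the concern, because it supposes that whoever decides entry can foresee which cases would be handled inappropriately.

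**4. Timing**

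The Methods text places randomisation at the positive result. The table's own header places Allocation at Day 0. Only the mark in the Allocation row points to Day -1, about 24 hours earlier.

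**The case against.** The case on the other side is substantial.

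- *The word is plural.* Several investigators are listed, and nothing says that one person makes the list, screens and enrols. The blinding statement could be read as implying a division of labour. This stands. It means that separation is unstated, not that it is absent.
- *There are real safeguards.* Envelopes are sealed, opaque and numbered; the sequence is unblocked, so earlier assignments do not predict the next; positive cultures are taken consecutively; and every specimen is assessed. These protect against guessing. They do not protect against someone who holds the list.
- *Exclusions leave little discretion.* They are origin outside long-term care, pregnancy, antibiotics at collection, and a known low neutrophil count. A reader might picture a sick-looking resident being kept out when the next report is modified, but no criterion turns on severity. Antibiotic status and neutrophil count do have to be looked up outside the culture result, so some room remains, but less than the 67 suggests.
- *The timeline mark may be a table-reading artefact.* The eligibility row carries column captions rather than entries, so the mark may have shifted. This cannot be settled from the text.

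A reader might also infer that allocating at receipt exposes the next assignment. It does not. It would mean exclusions made after allocation, which is a different problem. Nor do the documents support a count such as 100/0.30 = 333 allocations at receipt: the 30% is laboratory-wide, and its use for long-term care urine is an assumption. The Statistical methods section also limits the intention-to-treat set to specimens that were randomised and reported, although the Sample size section speaks of all patients randomised.

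**Conclusion.** The point holds in a limited form. The protocol states an arrangement in which one group generates the sequence, enrols and assigns, and it names no independent custodian. Concealment at entry is therefore not assured. The claimed blinding of investigators is not assured either, and this matters because they judge the primary outcome. A reader might go further and conclude that the envelopes fail or that the trial is unconcealed. The documents do not support that, because they do not say that the same individual performs these steps.

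The size of any bias is unknown. Under the assumptions shown, turning away about 1 to 8 specimens would create 1.3 to 8.7 spurious points. That is small against the planned 27.3, but enough to raise the false-positive chance in one direction from 2.5% to between 3.3% and 13.9%. The sample size is unaffected. This should be corrected because protection is cheap, not because bias has been demonstrated. The timeline mark is a separate, minor item to reconcile.

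**What to change.** Amend the Implementation and Blinding sections before recruitment:

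1. The sequence is generated, and the envelopes are filled, by an existing staff member who does not screen, enrol, collect data or assess outcomes. A laboratory staff member outside the study would serve. The graduate student would not, because that student collects, enters and analyses the data.
2. Eligibility, specimen accession number and time are written on the next numbered envelope before it is opened.
3. Investigators who assess outcomes have no access to the list or to opened envelopes. This gives the blinding statement a stated basis as far as the list and envelopes are concerned.

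Separately, check the Allocation mark in the timeline against the source table. Reconcile it with the table's Day 0 header and the Methods text, so that allocation follows the positive result and the eligibility check.

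Cost: a few sentences and possibly one table cell, with no extra specimens and no new staff. The downside is one written step per envelope.

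### The UTI/ASB diagnosis behind the primary outcome is made from charts two days after an unblinded report, with no symptom window fixed before the report, so it may depend on the arm

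*Combined protocol and SAP*

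**What the plan says.** Under Methods: Participants, interventions, and outcomes, a case counts as appropriate if a UTI is treated or an ASB is left untreated. The diagnosis is therefore half of the primary outcome.

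On timing, Data collection methods states that "a physician investigator will assess inpatients for the true diagnosis of UTI or ASB at two days after reporting". The Outcomes section has appropriateness judged from chart review no later than two days after the positive culture. The participant timeline puts the treatment decision and the appropriateness assessment both at Day 2.

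The UTI criteria rest largely on changeable signs such as fever, dysuria, frequency and mental status. The text does not say that these must be present at collection or before the report.

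Only the modified report carries the wording "This POSITIVE urine culture may represent asymptomatic bacteriuria or urinary tract infection. If urinary tract infection is suspected clinically, please call the microbiology laboratory". Under Blinding, physicians are unblinded and investigators are said to be blinded to assignment.

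The Sample size section raises diagnostic bias and answers it as follows: "Because true diagnosis may be biased by lack of access to clinical information, an intention to treat analysis including all patients randomized will be performed".

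**The concern.** A changed label flips the outcome with no change in care, and the label is given after the report has had time to act. There are two possible routes to a difference between arms. First, if the assessor relies on the resident's state at Day 2, treatment started in the meantime may have changed the signs. Second, the modified report prompts the physician to ask whether UTI is suspected, so symptoms may be sought and charted differently in that arm. An assessor masked to arm would still read the chart that resulted.

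If either route operates unequally, part of the observed difference in appropriateness is an artefact. Intention to treat keeps each specimen in its randomised arm but leaves a wrong diagnosis wrong. The only secondary efficacy outcome is the proportion of calls for the full report, so no planned efficacy comparison of treatment is free of the diagnosis. Data monitoring also stops the trial if the interim primary result is significant, so an artefact could end recruitment early.

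**Working it through.** **Inputs from the documents.** Error rates: "Accepting a risk of type 1 error of five percent, and a risk of type 2 error of twenty percent". Test: "a comparison of proportions between two groups (T test, two-sided analysis"). Design: "2 parallel groups with equal allocation, superiority analysis". Planning rates: "modified reporting increased the appropriateness of treatment from 29/55 (52.7%) to 44/55 (80.0"%). Share with ASB in the previous trial: 76/110 = 69%, so about 31% UTI.

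**The plan's own figure.** With p1 = 29/55 = 0.527, p2 = 0.800 and mean 73/110 = 0.664, the pooled formula gives

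n per arm = [1.960 × √(2 × 0.664 × 0.336) + 0.842 × √(0.249 + 0.160)]² / 0.273² = 45.9, so 46 per arm and 2N = 92.

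The unpooled formula gives 44 per arm and 2N = 88. The stated 90 lies between them, and 90/0.90 = 100. It rests on the 27.3-point difference, not on the stated text "for an absolute difference of +23"%. That mismatch is a separate matter.

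**Direction.** Four kinds of relabelling are possible:
- A treated UTI whose signs have resolved is read as ASB: scored inappropriate.
- A treated ASB has symptoms charted that support treatment: scored appropriate.
- An untreated UTI has few symptoms charted: scored appropriate.
- An untreated ASB has new signs by Day 2: scored inappropriate.

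These pull both ways, and the documents do not say which dominates in either arm.

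**Size of the first kind, under assumed rates.** Net shift = 0.31 × (difference between arms in the share of UTIs treated) × (share of treated UTIs relabelled). Assume that 100% are treated in the standard arm, 70% in the modified arm, and that relabelling is equal in both:
- 10% relabelled: 0.31 × 0.30 × 0.10 = 0.9 points
- 20% relabelled: 0.31 × 0.30 × 0.20 = 1.9 points
- 30% relabelled: 0.31 × 0.30 × 0.30 = 2.8 points

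With equal treated shares and equal relabelling, the net shift is zero.

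**What a net shift does to the test.** This is exact binomial enumeration of the two-sided uncorrected Pearson chi-squared test, 50 per arm, no interim look, with the shift applied to the modified arm.

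No true effect (52.7% in both arms), shift in that arm's favour:
- 0 points: 5.7% rejection
- 2.8 points: 6.6%
- 5 points (2.5 specimens of 50): 8.7%
- 10 points: 18.2%

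True rates 52.7% and 80.0%:
- no shift: 83.5% power
- 5 points against the modified arm: 64.7%
- 10 points against it: 43.3%
- 5 points in its favour: 95.0%

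The documents give no relabelling rate. The shifts of 5 and 10 points show sensitivity and are not estimates.

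**The case against.** The strongest objection is that the date of review is not the symptom window. The outcome is based on chart review, and fever or dysuria noted at collection is still in the chart after treatment. Many of the criteria describe acute or new onset, not persistence to Day 2. A careful assessor could classify from earlier entries, and the data collection form, which is not in the text available, may ask for dates. This stands: the documents do not show that any diagnosis is altered. But the visible text does not require use of the earlier entries, and leaving the choice open is the gap.

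A reader might go further and infer that the bias favours the modified report, because treated UTIs would be relabelled mainly where more are treated. The documents do not support this. Other kinds of relabelling run the opposite way, and nothing says that the standard arm treats UTI sooner. Only antibiotic use at collection is excluded and the report follows receipt by about 24 hours, so treatment may begin before the report in either arm.

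A reader might also take one arm's loss as the bias, for example 0.31 × 1.0 × 0.30 = 9.3 points. That is a gross figure; only the difference between arms biases the comparison. The 31% itself comes from acute-care inpatients without catheters, whereas this trial enrols long-term care residents and includes indwelling catheters.

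Finally, the protocol's stated worry is missing clinical information, not an effect of the arm. That is a fair reading, but intention to treat does not cure misclassification from either source.

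**Conclusion.** The point holds as a risk that the plan leaves open, not as a demonstrated bias. On the visible text, the diagnosis is assigned after an unblinded report, from charts kept by those who received it, with no window fixed before the report. Neither assessor blinding, taken at face value, nor intention to treat closes this.

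Size and direction are unknown. Under the assumptions in the working, the net shift is 0.9 to 2.8 points against a planning difference of 27.3, and the effect on false rejection is small (5.7% to 6.6%). It would matter more if charting differences added to it, since 5 points is only 2.5 specimens in an arm of 50. The case for acting rests on the low cost of the remedy.

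**What to change.** 1. In Data collection methods, state that for the main analysis UTI or ASB is classified from signs, symptoms and samples dated up to release of the report. Tests sampled before the report count even if resulted later, which covers blood cultures and white cell counts.
2. Record later signs separately and include them only in a sensitivity analysis.
3. Add a secondary outcome that needs no diagnosis: the proportion of specimens with any antibiotic treatment, by arm. Treatment decisions are already collected. It does not replace the primary outcome, because it cannot separate wanted from unwanted treatment.
4. Report the proportion labelled UTI by arm, which randomisation should make similar. The check is coarse: at 31% and 50 per arm the standard error of the difference is √(2 × 0.31 × 0.69 / 50) = 9.2 points, so a similar share is not proof of no bias.
5. Remove the statement that intention to treat addresses diagnostic bias. Keep the intention-to-treat analysis itself.

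The cost is a date limit on the existing chart abstraction and a few extra tabulations; the sample size is unchanged. There are two drawbacks. A few residents whose signs appear only after the report are classed by their earlier state in the main analysis, so one who is then treated would be scored inappropriate there; the sensitivity analysis covers them. Comparability with the earlier trial's definition, whose rates drive the sample size, is slightly reduced. These rules concern outcome scoring only, not care.

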Recognizing the inappropriate treatment of ASB to be a problem in acute care, a novel intervention was defined, in which identification and susceptibility results for positive urine culture results were not made available to physicians, unless the physician called the microbiology laboratory.(10) This “modified reporting” was associated with a reduction in the rate of antibiotic treatment of AB from 48% to 12% (number needed to report for benefit = 3) among non-catheterized inpatients, using historical controls.

A randomized, unblinded controlled trial was performed in acute care in St. John's, among patients without indwelling catheters, using the same intervention.(11) Results of positive urine cultures from 110 consecutive inpatients at two urban hospitals were randomised to

standard report or modified report. Specimens randomized to the modified report were reported as follows: "This POSITIVE urine culture may represent asymptomatic bacteriuria or urinary tract infection. If urinary tract infection is suspected clinically, please call the microbiology laboratory for identification and susceptibility results."

Exclusion criteria were age less than 18 years, pregnancy, presence of an indwelling urinary catheter, samples from patients already on antibiotics, neutropenia, or admission to an Intensive Care Unit. Patients were followed for seven days, and physician treatment decisions were observed. 76/110 (69%) of positive urine cultures represented ASB. The proportion of appropriate treatment (UTI treated plus ASB not treated) was higher in the modified arm than in the standard arm (44/55 (80.0%) vs 29/55 (52.7%), absolute difference=-27.3%, RR=0.42, p=0.002, Number needed to report for benefit=3.7).

There were two bacteremias in the modified report group, and one bacteremia in the standard report group, none of which were considered related to the intervention. There were two deaths in the modified report group, and one death in the standard report group, none of which were considered related to the intervention. Based on this trial, the intervention was considered safe over 7 days of followup, and effective to reduce inappropriate treatment, but further study would be required among populations excluded from the trial.

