Urine culture is reported according to laboratory protocol by licenced medical laboratory technologists, in categories of significant growth, non-significant growth, and no growth, based on quantity of growth and number of bacterial types detected. Antimicrobial susceptibility is reported according to laboratory protocol, including selected first and second-line antibiotics, as susceptible, intermediate or resistant. Drug cost and dosage suggestion are provided.

Data collection form attached.

Data management

Data collection will use a paper case report form, and entered into a trial database by a graduate student. Variables will be coded appropriately. The dataset will be protected using a

password and stored on a laptop computer during data entry. After data entry is completed, data integrity will be reviewed by a second investigator, and then the dataset will be locked for analysis.

Statistical methods

All specimens randomised and reported will be included in the Intention-to-treat (ITT) analysis. Specimens inappropriately included will be excluded from the Per-protocol (PP) analysis. The proportion of appropriate treatment will be compared using two-sided Pearson chi squared test (SPSS 23.0, IBM, USA). Adjusted analysis may be performed if appropriate. A subgroup defined as specimens in which physicians requested complete reporting will be analysed for appropriateness, compared to the standard reporting arm. Missing data will not be imputed.

Data monitoring

A data monitoring committee will not be used, as a single investigator will assume responsibility for data quality. A single interim analysis at approximately 50% recruitment will be performed, and the study stopped if the primary outcome achieves statistical significance.

Harms

Serious adverse events will be reported to the ethics committee within 24 hours. Adverse events will be collected by the investigators at day 2, day 7 and day 30. Patients with adverse events will be provided care in hospital.

Auditing

There will not be auditing of trial conduct during or after the trial.

Research ethics approval

The protocol will be submitted to the Provincial Health Research Ethics Board.

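### The planned subgroup sets modified-report specimens whose physician requested results against the whole standard arm; this is not a randomised comparison and can show a difference when reporting has no effect

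*Combined protocol and SAP*

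**What the plan says.** After the ITT and per-protocol analyses, the Statistical methods section adds: "A subgroup defined as specimens in which physicians requested complete reporting will be analysed for appropriateness, compared to the standard reporting arm". The comparator is named, and it is the whole standard arm.

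Four other places bear on it:

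- Methods: Participants, interventions, and outcomes: "Physicians receiving modified reports will have the option to call the laboratory to receive complete results, or not". The Interventions section says that the standard report already carries count, identification and susceptibility, so that arm has nothing to request.
- Interventions, text of the modified report: "If urinary tract infection is suspected clinically, please call the microbiology laboratory".
- Methods, outcome definition: "Appropriate therapy is defined as any treatment for UTI, or no treatment for ASB".
- Outcomes: "Proportion of calls from physicians requesting complete report" is the only secondary efficacy outcome. Data collection methods adds: "Frequency of physician calls requesting complete reporting will be recorded".

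No section calls the subgroup comparison non-randomised, exploratory or descriptive. None defines a matching subset of the standard arm or a method for handling the selection. Statistical methods allows for adjusted analysis, but names no covariates and does not tie it to this subgroup.

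**The concern.** Randomisation makes the two full arms comparable. It does not make a self-selected part of one arm comparable with the whole of the other. Membership here is decided after allocation, by the physician, in one arm only, and the request is itself an outcome of the intervention.

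The selection is also linked to the endpoint. Appropriateness is fixed by two facts: whether the specimen represents UTI or asymptomatic bacteriuria (ASB), and whether it was treated. A physician who calls because UTI is suspected tends to bring in UTI specimens. A physician who calls because a drug has to be chosen brings in treated specimens. Either way, callers can differ from the standard arm in case mix or treatment even if the type of report changes no decision.

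The resulting number cannot separate an effect of modified reporting from who chooses to call. A reader could take a positive gap as added evidence of efficacy, or a negative one as evidence of harm. The protocol intends publication and possible routine use of the intervention, and gives no warning.

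**Working it through.** The plan gives no figure for this subgroup, so the check asks what the comparison would show if reporting had no effect on any treatment decision.

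**Inputs from the documents (previous acute-care trial, not long-term care)**
- ASB share (Background and rationale): "76/110 (69%) of positive urine cultures represented ASB". So pa = 76/110 = 0.691 and the UTI share is pu = 34/110 = 0.309.
- Standard-arm appropriateness (Sample size): A0 = 29/55 = 0.527.

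**Assumed inputs**
- Share of UTI treated: tu = 0.90, varied from 0.80 to 1.00.
- All call rates.

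**Share of ASB treated, ta.** From A0 = pu·tu + pa·(1 − ta):
ta = 1 − (0.527 − 0.309 × 0.90)/0.691 = 0.639.

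**Case 1: calling follows diagnosis.** Let cu and ca be the call rates for UTI and ASB.
- UTI share among callers: s = pu·cu/(pu·cu + pa·ca)
- Appropriate among callers: s·tu + (1 − s)(1 − ta)

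For cu = 0.8, ca = 0.2: s = 0.2473/(0.2473 + 0.1382) = 0.642. Appropriate = 0.642 × 0.90 + 0.358 × 0.361 = 0.707. Gap = 0.707 − 0.527 = +17.9 points.

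| cu, ca | tu = 0.80 | tu = 0.90 | tu = 1.00 |
|---|---|---|---|
| 0.8, 0.4 | +6.4 | +8.8 | +11.2 |
| 0.6, 0.2 | +10.4 | +14.2 | +18.1 |
| 0.8, 0.2 | +13.1 | +17.9 | +22.7 |
| 0.5, 0.1 | +15.1 | +20.6 | +26.1 |
| 0.9, 0.1 | +19.4 | +26.5 | +33.7 |
| 0.5, 0.5 | 0 | 0 | 0 |

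**Case 2: calling follows intent to treat.** Let ct and cn be the call rates for treated and untreated specimens.
- Appropriate among callers: [ct·pu·tu + cn·pa·(1 − ta)] / [ct·(pu·tu + pa·ta) + cn·(pu·(1 − tu) + pa·(1 − ta))]

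With tu = 0.90, the four cells are UTI treated 0.278, UTI untreated 0.031, ASB treated 0.442 and ASB untreated 0.249. For ct = 1, cn = 0: 0.278/(0.278 + 0.442) = 0.386, a gap of −14.1 points.

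| ct, cn | Gap (tu = 0.90) |
|---|---|
| 0.8, 0.4 | −5.9 |
| 0.6, 0.2 | −8.3 |
| 0.8, 0.2 | −9.6 |
| 0.5, 0.1 | −10.5 |
| 0.9, 0.1 | −12.0 |
| 1, 0 | −14.1 |

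**Sensitivity to the ASB treatment rate.** Background and rationale also gives a 48% ASB treatment rate, from the historical-control study.
- ta = 0.48 with A0 kept at 0.527 implies tu = (0.527 − 0.691 × 0.52)/0.309 = 0.544. The 80%/20% gap is +0.8 points by diagnosis and −11.5 by treatment.
- ta = 0.48 with tu kept at 0.90 gives a control rate of 0.309 × 0.90 + 0.691 × 0.52 = 0.637. The 80%/20% gap is +12.6 points by diagnosis (0.764) and −11.7 by treatment.

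**Case 3: mixed calling that cancels.** Call rates of 80% for treated UTI, 50% for treated ASB and 10% for untreated specimens, with tu = 0.90: (0.2225 + 0.0249)/(0.2225 + 0.0031 + 0.2209 + 0.0249) = 0.525, a gap of −0.2 points.

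**Effect on a test.** The subgroup sentence names no test. If the protocol's Pearson chi-squared test were used, a simulation with no reporting effect (20,000 runs, 50 per arm from the target of 100, tu = 0.90) gives these rejection rates at the nominal 5% level:

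| Calling pattern | Callers vs standard arm |
|---|---|
| 90% of UTI, 30% of ASB | 22% |
| 80% of UTI, 20% of ASB | 27% |
| Only when treating | 26% |
| 50% of both diagnoses | 5% |

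The ITT comparison rejects in about 6% of runs under all four patterns.

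**The case against.** The strongest reply is that the plan makes no causal claim for this analysis. It is called a subgroup, it is neither a primary nor a secondary outcome, it plays no part in the interim stopping rule, and its sentence names no test. On that view only a label is missing, and adding one would be enough. The first part is accurate, and it is why this is not a threat to the trial's main result. But the sentence fixes a cross-arm comparison of the trial's own endpoint. A label would warn the reader and still leave a number with no clear meaning.

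A second reply is that the magnitude is built on assumptions. The call rates and the 90% are invented. The 34/110 pools both arms of the previous trial, whereas 52.7% is its standard arm alone. That trial also excluded indwelling catheters, which this one includes. All of this stands, and the results include values near zero. So the figures show only that a sizeable spurious gap is possible in either direction; they do not predict one for this trial. The validity point needs no particular rate.

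Third, the protocol says that call frequency will be recorded but does not state that calls are linked to specimens, and the data collection form is not visible. That is a fair caution, but the planned subgroup already requires such a link.

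**Conclusion.** The concern holds. As written, the analysis compares a post-randomisation, self-selected part of one arm with the whole of the other, selected on something linked to the endpoint, and nothing else in the document corrects or flags this.

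The size and direction of the bias cannot be known from the documents. With no effect of reporting, the previous trial's case mix and control rate, and an assumed 90% of UTI treated, the illustrated gap is +9 to +27 points if calling follows diagnosis (+6 to +34 for 80% to 100% of UTI treated) and −6 to −14 points if it follows intent to treat. Other inputs bring it close to zero. At the upper end it is comparable with the previous trial's 80.0% − 52.7% = 27.3-point effect. In these scenarios the gap is zero when calling is unrelated to both diagnosis and treatment, which is not what the report text asks for; otherwise it is near zero only when influences happen to offset.

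The primary ITT comparison, the sample size and the safety outcomes are not affected.

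**What to change.** In Statistical methods, delete the comparison of callers with the standard arm. In its place, plan a description within the modified arm of callers and non-callers: number of specimens, share with UTI, proportion treated and proportion appropriate. State that the two groups are formed by physician choice after randomisation, that the summary is descriptive and non-randomised, and that neither group will be tested against standard reporting.

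The cost is one sentence of protocol wording, best changed before the data are analysed. Diagnosis and treatment are already collected, and the specimen-level record of calls is already needed for the planned subgroup; confirm that the data collection form captures it. What is lost is a cross-arm summary that has no causal interpretation.
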